#### Figure 3 McBurney's Point

Administration of UV1 should be done **10 to 15 minutes** *after* the administration of sargramostim. The UV1 is to be administrated at the exact same site as the sargramostim.

Allergic reactions may occur after sargramostim and UV1 injections. Therefore, patients should remain at the site for observation for at least 4 hours after each UV1 injection.

Nivolumab and ipilimumab are administered intravenously according to the label and administration is to be started at least 1 hour after the injection of UV1.

Patients in the experimental arm will receive 8 UV1 vaccinations over 4 cycles of nivolumab and ipilimumab. The UV1 vaccination will be administered alone on Days 1, 3 to 7 (2 UV1 vaccinations), and 26, and in combination with nivolumab and ipilimumab on Days 10, 31, 52, and 73.

Patients in the control arm will receive 4 cycles of nivolumab and ipilimumab, on Days 1, 22, 43, and 64.

The administration of sargramostim, UV1, nivolumab, and ipilimumab must be recorded in the patients' medical files and the appropriate section of the electronic Case Report Form (eCRF). The reason for dose interruption, reduction, or omission will also be recorded in the medical files of patient and later in the eCRF. This information will be used to assess compliance with treatment.

Following the induction therapy, patients in both treatment arms will start maintenance therapy and receive nivolumab at a dose of 480 mg Q4W according to the label. It is not allowed to use any other dose of maintenance therapy (eg, 240 mg Q2W). Nivolumab is the standard of care and should be monitored according to the institutional practice (including routine blood sampling).

# 6.1.6 Preparation/Handling/Storage/Accountability

Unless stated otherwise, sargramostim, nivolumab, and ipilimumab should be stored and handled according to the prescribing information. All handling of study drug should be compliant with normal handling of sterile products for injection.

UV1 and sargramostim will be supplied to the study sites by the Sponsor. Nivolumab and ipilimumab will be sourced locally by the study sites.

The Investigator or designee must maintain accurate records of study drugs received from the Sponsor, and documentation of preparation and administration of sargramostim, UV1, nivolumab, and ipilimumab. Drug name, dose, and batch number/study treatment ID (if required) will be documented for all study drugs administered.

Only patients randomized in the study may receive study drug and only site staff authorized by the Investigator may supply or administer the study drug(s). All study drugs must be stored in a secure, environmentally controlled, and monitored (manual or automated) area with access limited to the Investigator and authorized site staff.

The Investigator or designee must maintain a log to confirm appropriate temperature conditions have been maintained during storage for all study drugs received by the Sponsor and any discrepancies must be reported and resolved before use of the study drug.

The Investigator or designee is responsible for study drug accountability, reconciliation, and record maintenance (ie, receipt, reconciliation, and final disposition records).

Where appropriate facilities and procedures for drug destruction exist and prior approval from the site monitor has been received, site personnel will account for appropriate destruction.

### 6.1.7 Treatment of Allergic Reactions to UV1 Vaccination

Investigators are advised to follow the standard treatment of anaphylaxis and allergies per local guidelines.

## 6.1.8 Dose Modification

Dose modification of sargramostim or UV1 is not allowed in this study. Nivolumab and ipilimumab should be dosed according to the label.

#### 6.1.9 Overdose

There is no information on overdose of UV1 vaccination, but the distribution route and degradation of the UV1 vaccination suggests that there would be few consequences, if any. Therefore, in the event of an overdose, the patient should be observed for any reactions and treated symptomatically.

There is no information on overdose with ipilimumab and nivolumab, given either as monotherapies or concomitantly. In case of overdosage, patients must be closely monitored for signs or symptoms of adverse reactions and appropriate symptomatic treatment instituted.

# 6.2 Concomitant Medication

Any medication or vaccine (including over-the-counter or prescription medicines, vitamins, and/or herbal supplements) that the patient is receiving at the time of randomization or receives during the study must be recorded along with:

- reason for use
- dates of administration including start and end dates
- dosage information including dose and frequency.

The medical monitor should be contacted if there are any questions regarding concomitant or prior therapy.

All ongoing and new medications will be recorded from 28 days prior to randomization, until 30 days after the last dose of induction, or until new anticancer treatment is initiated (whichever comes first). Ongoing and new medications shall also be recorded in connection with any SAEs.

## 6.2.1 **Prohibited Medications During Induction Period**

The following medications and vaccinations are not allowed during the Induction period:

- Immunosuppressive agents
- Systemic corticosteroids >10 mg daily prednisone equivalent (except as stated in Section 6.2.2)
- Any concurrent anticancer therapy (ie, chemotherapy, hormonal therapy, immunotherapy, radiation therapy, or investigational agents for treatment of cancer). Radiation therapy to a symptomatic lesion may be allowed after consultation with the sponsor. Supportive care for disease-related symptoms, including bisphosphonates and denosumab, may be offered to all patients in the study.
- Live vaccines within 30 days prior to the first dose of induction therapy and while participating in the study. Examples of live vaccines include, but are not limited to, measles, mumps, rubella, chicken pox, yellow fever, seasonal flu, H1N1 flu, rabies, BCG, and typhoid vaccine.
- Other investigational agents.

# 6.2.2 Permitted Medications During Induction Period

Patients are permitted to use topical, ocular, intra-articular, intranasal, and inhalational corticosteroids (with minimal systemic absorption). Physiologic replacement doses of systemic corticosteroids, a brief course of corticosteroids for prophylaxis (e.g. contrast dye allergy) or for treatment of non-autoimmune conditions is permitted even with >10 mg/day prednisone equivalents.

# 6.2.3 New Anticancer Treatment

Details of any new anticancer treatments, from the time of the last dose of induction therapy until the earliest of either 70 PFS events reached or 18 months post last patient randomized, must be recorded in the eCRF. The reason for end of treatment for IMP and NIMP (nivolumab and ipilimumab) must be recorded.

### 6.3 Treatment After Progressive Disease

Clinical evidence indicates that some patients treated with immune system-stimulating agents may develop PD by conventional response criteria (ie, pseudo-progression per iRECIST), before demonstrating clinical overall responses and/or SD. This may be explained by:

- Enhanced inflammation within tumors leading to increased tumor size which would appear as an enlarged index lesion and as newly visible small non-index lesions. Over time, both the malignant and inflammatory portions of the mass may then decrease leading to overt signs of clinical improvement.
- Initially, the kinetics of tumor growth may outpace anti-tumor immune activity. With sufficient time, the anti-tumor activity will dominate and become clinically apparent.

For patients who have initial radiological evidence of PD by RECIST 1.1 or iUPD (per iRECIST), it is at the discretion of the Investigator to keep the patient on induction/maintenance therapy (in the absence of clinical deterioration) until repeat imaging is obtained 4 to 8 weeks afterwards (iRECIST-based management). The decision to continue induction/maintenance therapy should only be made if the patient is assessed to be clinically stable, deriving clinical benefit, and tolerating the treatment.

At a minimum, patients must meet the following criteria for continuing induction/maintenance therapy after PD per RECIST 1.1/iUPD is identified:

- Absence of worsening symptoms and signs (including worsening of laboratory values)
- No decline in ECOG performance status
- Absence of rapid PD or of progressive tumor at critical anatomical sites (eg, cord compression) requiring urgent alternative medical intervention.

If repeat imaging fails to demonstrate iCPD (by iRECIST) and the patient continues to be clinically stable, induction/maintenance therapy should continue per protocol.

If repeat imaging demonstrates iCPD, induction/maintenance therapy should be discontinued.

The continuation/discontinuation of nivolumab as maintenance therapy will be recorded in the patients' medical file and in the eCRF.

# 7 Study Duration and Schedule of Activities

This study will consist of 3 phases: Screening, an Induction period, and a Follow-up period. The Follow-up period includes safety, response, and survival follow-up visits.

	Screening	Induction period								Follow-up period			
Visit/Cycle		V1	V2	+ 3	V4 C1	V5	V6 C2	V7 C3	V8 C4	Safety follow- up	Response follow-up	Survival follow-up a	Survival follow- up a
Visit window		0	(	)	± 2d	± 2d	± 2d	± 2d	± 2d	+7d	±1w	±1w	+2w
Days/Weeks	D -28 to -1	D1	D3 UV1 vac Conse dosing c allo	3-7 cinations cutive lays not wed	D10	D26	D31	D52	D73	30 days post last dose of induction therapy	10w post last dose of induction therapy then every 8w for 32w. Subsequent visits every 12w until iCPD per iRECIST or PFS cut-off date reached	Every 12w from iCPD per iRECIST until PFS cut-off date reached	From time of the PFS cut-off date reached: Every 6 months for 2 years
Signed consent	Х												
Eligibility criteria	Х												
Medical history	Х												
Vital signs & ECOG	Х	Х			Х		Х	Х	Х	Х			
Physical examination	Х									Х			
Local lab analysis (all patients) b													
• Hematology & chemistry m	Х	Х			Х	Х	Х	Х	Х	Х			
Hepatitis B & C virus	Х												
Pregnancy test c	Х				Х		Х	Х	Х	Х			
Central lab sampling (all patients) d		Х					X	Х		Х	X (2 nd visit only)		
Randomization e		Х											
Treatment:			1			1			1	L	1		
UV1 vaccination		Х	Х	Х	Х	Х	Х	Х	Х				
Nivolumab					Х		Х	Х	Х	N	ivolumab 480 mg Q4W according to	label (maintenance the	erapy) f
Ipilimumab					Х		Х	Х	Х				
Adverse Events g	Х	Х	Х	Х	Х	Х	Х	Х	Х	Х	X	Х	
Concomitant medication h	Х	Х	Х	Х	Х	Х	Х	Х	Х	Х			
Subsequent anticancer treatment										Х	Х	Х	
Survival status												Х	Х
Tumor imaging i	FIRST tumor imagin SECOND tumor ima SUBSEQUENT tumo ADDITIONAL tumo	T tumor imaging during Screening at Day -14 to -1 DND tumor imaging at Week 12 and THIRD tumor imaging at Week 19 post randomization SEQUENT tumor imaging every 8 weeks for 32 weeks and then every 12 weeks until PD per iRECIST or until PFS cut-off date is reached (whichever comes first) JITIONAL tumor imaging if premature treatment discontinuation due to any cause											
Extended Explorator	y Cohort (40 patients	i) i											
Signed consent (exploratory	Х												
Fecal sample	X												
Tumor biopsy (FFPE &	Х									Х			
DNA & SNP		Х											
PBMC		Х					Х			X	X (2 nd visit only)		
DTH		Х					X	Х		Х	X (2 nd visit only)		

- Abbreviations: AE = adverse event; C = cycle; D/d = day; DNA = deoxyribonucleic acid; DTH = delayed-type hypersensitivity; ECOG = Eastern Cooperative Oncology Group; FFPE = formalin fixed, paraffin embedded; ICF = Informed Consent Form; iCPD = immune confirmed progressive disease; iRECIST = immune Response Evaluation Criteria in Solid Tumors; PFS = Progression Free Survival; PBMC = peripheral blood mononuclear cell; Q4W = every 4 weeks; SAE = serious adverse event; SNP = single nucleotide polymorphisms; V = visit; w = week.
- a Patients with iCPD per iRECIST will be discontinued from treatment and will proceed into the survival follow-up phase and be contacted per phone (or, at the Investigator's discretion visit the hospital) every 12 weeks until PFS cut-off date is reached (earliest of either 70 PFS events or 18 months post last patient randomized). From the PFS cut-off date, the survival follow-up visits will continue every 6 months for 2 years.

b Local lab analysis for verification of eligibility criteria is required during Screening at Day -14 to -1. See Table 7 for protocol-required safety laboratory assessments.

e WOCBP require negative pregnancy test within 72 hours prior to randomization, at Days 10, 31,52, 73 and at the safety follow-up visit. Additional pregnancy tests according to local regulations for treatment of nivolumab and ipilimumab, if required.

dSee Table 8 for collection of samples for exploratory analysis.

e Patients can be randomized up to 3 days (from Day -3 until Day 1) prior to first dosing on Day 1 but only after all Screening assessments are completed.

- f Patients will start maintenance therapy 6 weeks after last dose of induction therapy.
- g From signing of the ICF until the first dose of induction therapy only AEs/SAEs caused by study-specific procedures should be reported. All non-serious AEs should be reported from the first dose of induction therapy until 30 days after the last dose of induction therapy, or until new anticancer treatment is initiated (whichever comes first). All SAEs should be reported from the first dose of induction therapy until the PFS cut-off date is reached or until new anticancer treatment is initiated (whichever comes first).
- h All ongoing and new medications will be recorded from 28 days prior to randomization, until 30 days after the last dose of induction, or until new anticancer treatment is initiated (whichever comes first). Ongoing and new medications shall also be recorded in connection with any SAEs.
- i Tumor imaging should be performed regardless of treatment stop or delays and within a visit window of ± 7 days. Tumor imaging will be performed using CT/MRI scans of the chest, abdomen, and pelvis. CT scans are the required modality for measurable disease unless a patient has a clinical condition (e.g. severe contrast allergy) or the lesions are better visualized through the use of MRI. The same imaging technique has to be used in a patient throughout the study. If an unscheduled CT/MRI is performed during the study, subsequent protocol planned CTs/MRIs should be performed unless the time interval between the CTs/MRIs is ≤4 weeks.
- j A cohort of approximately 40 patients at selected sites will be asked to volunteer for additional biological sampling and analysis. See Table 9 and Table 10 for collection of samples and DTH for the Extended Exploratory Cohort.
- k If the patient has only one target lesion, the biopsy should be taken either subsequent or at least 7 days prior to the screening imaging scan.
- UV1 without sargramostim injected intradermally in the skin of the anterior forearm. Patient will measure and record the skin reaction 48±4 hours after the injection.
- m It is recommended to have blood sampling on day of treatment. If the sampling was not done on the day of treatment and the most current Liver Function Test (LFT) results warrant a safety concern, the site must repeat the LFT panel on the day of treatment and review the results prior to study drug administration.

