#### Table 6Schedule of Activities – Control Arm

	Screening		Induction	therapy		Follow-up period				
Visit/Cycle		V1 C1	V2 C2	V3 C3	V4 C4	Safety follow-up	Response follow-up	Survival follow- up a	Survival follow- up a	
Visit window		0	± 2d	± 2d	± 2d	+7d	±1w	±1w	+2w	
Days/Weeks	D -28 to -1	Dl	D22	D43	D64	30 days post last dose of induction therapy	10w post last dose of induction therapy then every 8w for 32w. Subsequent visits every 12w until iCPD per iRECIST or PFS cut-off date reached	Every 12w from iCPD per iRECIST until PFS cut-off date reached	From time of thePFS cut-off date reached: Every 6 months for 2 years	
Signed consent	Х									
Eligibility criteria	X									
Medical history	X									
Vital signs & ECOG	X	Х	Х	Х	Х	Х				
Physical examination	Х					Х				
Local lab analysis (all patients) b			4	1						
• Hematology & chemistry  )	Х	Х	Х	Х	Х	Х				
Hepatitis B & C virus	Х									
Pregnancy test c	Х	Х	Х	Х	Х	Х				
Central lab sampling (all patients) d		Х		Х	Х	Х	X (2 nd visit only)			
Randomization e		Х								
Treatment:										
Nivolumab		Х	Х	Х	Х	Nivolumab 480 mg Q4W according to label (maintenance therapy) f				
• Ipilimumab		Х	Х	Х	Х					
Adverse Events g	Х	Х	Х	Х	Х	Х	Х	Х		
Concomitant medication h	Х	Х	Х	Х	Х	Х				
Subsequent anticancer treatment						Х	Х	Х		
Survival status								Х	X	
Tumor imaging i	FIRST tumor i SECOND tum SUBSEQUEN first)	imaging dur or imaging a T tumor ima	ing Screeni at Week 12 aging every	ng at Days and THIR 8 weeks fo	-14 to -1 D tumor in or 32 week	maging at Weeks and then ev	ek 19 post randomizatio ery 12 weeks until PD p	on per iRECIST or until the PFS cut-c	off date is reached (whichever comes	
Extended Exploratory Coho	ort (40 patients) j									
Signed consent (exploratory cohort)	Х									
Fecal sample	X									
Tumor biopsy (FFPE & snap-frozen) k	X					Х				
DNA & SNP		Х								
PBMC		Х		Х		Х	X (2 nd visit only)			

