#### Permanent Discontinuation of Induction Therapy Due to Safety Reasons

If due to safety reasons, all induction therapies are discontinued, the patient will complete the safety follow-up visit 30 to 37 days after the last dose of induction therapy. Thereafter, the

patient will continue with the response follow-up visits (10 weeks post last dose of induction therapy).

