#### Permanent Discontinuation of Induction Therapy Due to Progressive Disease

If, during the Induction period, a patient has PD confirmed by a repeat CT/MRI scan according to iRECIST (iCPD), all induction therapy will be discontinued and the patient will complete the safety follow-up visit 30 to 37 days after the last dose of induction therapy. Further anticancer treatment will be given at the Investigator's discretion. If anticancer treatments other than nivolumab are planned to start prior to 30 days after the last dose of induction therapy, the safety follow-up visit will be performed as soon as possible following the confirmed PD. The patient will thereafter continue into the survival follow-up.

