## 7.3.1 Safety Follow-up Visit

The safety follow-up visit should be conducted 30 to 37 days after the last dose of induction therapy. If anticancer treatments other than nivolumab are planned to start prior to 30 days after the last dose of induction therapy, the safety follow-up visit will be performed before the initiation of new anticancer treatment if possible.

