### 8.1 Efficacy Assessments

#### 8.1.1 Assessment of Tumor Response

#### 8.1.1.1 Tumor Imaging

Tumor imaging will be performed as detailed in the schedule of activities (Table 5 and Table 6) and should not be adjusted for dosing delays. It is important that patients are assessed according to the intended scanning schedule to prevent bias in analysis that may occur if one treatment arm is assessed differently compared to the other. If an unscheduled CT/MRI is performed during the study, subsequent protocol planned CTs/MRIs should be performed unless the time interval between the CTs/MRIs is <4 weeks.

Mandatory tumor imaging consists of:

• Contrast enhanced CT or MRI of chest, abdomen, and pelvis and all other known sites of disease. The CT scans are the preferred modality for measurable disease unless a patient has a severe iodine contrast allergy or other clinical condition that precludes optimal CT imaging, or the lesions are better visualized through the use of MRI. An MRI is the preferred modality for central nervous system (CNS) imaging in the case of suspected new CNS involvement. For a given patient, the same imaging modality should be used throughout the entire study to allow for comparability of lesions over time

- A CT or MRI of other body regions where lesions are present or suspected and can be visualized on CT or MRI (does not apply to superficial skin lesions). Once a lesion has been identified and documented with CT/MRI scanning, follow-up CT/MRI scans must be consistently repeated at all subsequent tumor assessment timepoints
- Digital photography and documentation with label and ruler of all skin lesions

All scheduled tumor images will be submitted for BICR. In addition, images that are obtained at an unscheduled timepoint and which relate to tumor assessment should also be submitted for BICR. Further details on tumor imaging and data transfer will be provided in a separate Imaging Guidance document.

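### Table 5 orders an extra scan when treatment stops early in the experimental arm, and Table 6 as extracted has none for control: a small bias in PFS dating, mainly against UV1, to be reconciled

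*Combined protocol and SAP*

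**What the plan says.** Both arms share one planned imaging schedule (Section 4.1): Weeks 12 and 19 after randomization, then every 8 weeks for 32 weeks, then every 12 weeks. Footnote i under both Table 5 and Table 6 keeps planned imaging going after treatment stops, within 7 days either side.

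The Table 5 row (experimental arm) has four lines: first, second/third, subsequent, and an additional line ordering "tumor imaging if premature treatment discontinuation due to any cause". It sets no deadline and does not say whether the stop of UV1, of the checkpoint inhibitors, or of all of them is the trigger.

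The Table 6 row (control arm) survives extraction only as nine cell fragments. The cell holding the line openings contains "SECOND tum SUBSEQUEN first". The fragments rejoin into the first, second/third and subsequent lines, with nothing left over.

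Section 8.1.1.1 explains that the schedule must be kept "to prevent bias in analysis that may occur if one treatment arm is assessed differently compared to the other". It also says that "images that are obtained at an unscheduled timepoint and which relate to tumor assessment should also be submitted for BICR". Section 9.4.2.1 defines primary PFS by central-review progression. Section 8.1.1.1 adds: "Further details on tumor imaging and data transfer will be provided in a separate Imaging Guidance document". Neither that guidance nor a stand-alone detailed SAP is among the documents supplied.

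**The concern.** Progression is dated by the scan that shows it. If an experimental patient who stops early is scanned at once, while a comparable control patient waits for the next planned scan unless the site orders one, the same biology is dated earlier in one arm. Blinded reading does not correct this, because the reader is blind to treatment but the scan date is fixed by the schedule. At stake are the primary hazard ratio and the power of a trial built on 70 events. The instruction would also go against the protocol's own reason for holding both arms to the same scans.

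**Working it through.** **1. The plan's own figure.** Events = 4(z₀.₉₀ + z₀.₈₀)² / (ln 0.60)² = 4(1.282 + 0.842)² / 0.261 = 69.1, rounded up to 70. This agrees with Section 9.2 and is not in dispute. The standard error of the log hazard ratio at 70 events is about 2/√70 = 0.239.

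**2. Is the scan ordered for control anywhere else?** The Table 6 footnotes, Section 4.1, Section 7.2.1 (safety, progression, and patient or investigator decision), Section 7.3.2 and Section 8.1.1.1 order no discontinuation scan for control. Table 5 is its only source.

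**3. What starts the scan?** Section 7.2.1 frames its safety rule as "If due to safety reasons, all induction therapies are discontinued", so stopping all induction therapy is the likelier trigger. That can happen in both arms. The same section lets UV1 stop alone, which cannot happen in control, but Table 5 does not say that this counts.

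**4. How much earlier?** Week 12 is Day 84, window Days 77 to 91. If the scan waits for the safety visit ("The safety follow-up visit should be conducted 30 to 37 days after the last dose of induction therapy"), it falls as follows:
- last dose Day 10: Days 40–47, which is 37–44 days before Day 84;
- last dose Day 31: Days 61–68, which is 16–23 days before;
- last dose Day 52: Days 82–89, inside the Week 12 window, so no real lead.

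**5. Simulation A: stopping unrelated to progression.** 77 per arm, 15-month accrual, cut-off 18 months after the last randomization, pooled plateau about 54–55%, Cox model, one-sided 0.10, 4,000 paired replicates. The documents give neither a discontinuation rate nor a scan deadline, so both are assumed. At 20/40/60% stopping and true HR 0.60:
- scan within 7 days of stopping: HR ratio 1.005/1.011/1.016; power 0.788/0.779/0.773, against 0.792 with identical schedules; 1.4 to 4.3 events dated about 32 days earlier;
- scan at the safety visit: 1.004/1.008/1.013; power 0.789/0.782/0.777;
- stops spread to Day 365: 1.001/1.003/1.004;
- half of control stoppers also scanned: HR up 0.2–0.8%.

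Under no effect, one-sided rejection goes from 0.094 to 0.083–0.094.

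**6. Simulation B: linked stopping added.** 154 patients 1:1, plateau averaging 54.5%, planned imaging continuing, planned scans within 4 weeks skipped. In the linked cases, half of the early progressors who discontinue stop within 3 weeks of progression. Each row compares no extra scan with an extra scan in the experimental arm only; the last column is one-sided rejection.

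| True HR | Stopping | Method | Estimated HR | Ratio | Rejection, % |
|---|---|---|---|---|---|
| 0.60 | 20% unrelated | log-rank | 0.576 → 0.581 | 1.009 | 80.5 → 79.6 |
| 0.60 | 60% unrelated | Cox | 0.615 → 0.624 | 1.015 | 79.2 → 77.3 |
| 0.60 | 60% linked | Cox | 0.618 → 0.639 | 1.034 | 76.7 → 71.7 |
| 0.60 | 60% linked | log-rank | 0.578 → 0.611 | 1.057 | 79.2 → 74.0 |
| 1.00 | 60% unrelated | Cox | 1.003 → 1.022 | 1.019 | 8.7 → 7.6 |
| 1.00 | 60% linked | Cox | 1.002 → 1.045 | 1.043 | 8.2 → 5.9 |
| 1.00 | 60% linked | log-rank | 1.004 → 1.051 | 1.047 | 9.6 → 7.0 |

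The log-rank rows use the one-step HR estimate. Monte Carlo error is about 1 point per rate. With the extra scan in both arms, power in the fourth row is 79.8%.

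**7. Scale.** At true HR 0.60, 60% linked stopping moves the log HR by ln 1.034 = 0.033 (Cox) to ln 1.057 = 0.055 (log-rank), which is 14 to 23% of one standard error. The largest unrelated case shown, ln 1.019 = 0.019, is about 8%.

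**8. Does the remedy work?** In simulation A (within-7-day case, no scans skipped), dating progression first seen on the extra scan to the next planned assessment returns the ratio to 1.000 and power to 0.792.

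**The case against.** The strongest objection is that the missing line may be a conversion artefact. In Table 5 the labels for exploratory-cohort consent and for tumor biopsy have lost their second lines, which Table 6 keeps. A last line can therefore vanish without trace, and an additional line in Table 6 would come last. Those losses are in the other table and prove nothing about Table 6, but the point is conditional on a page check.

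Second, the gap is partly contained. Planned imaging continues after a stop in both arms. Stops for confirmed progression already involve a repeat scan in both: "a patient has PD confirmed by a repeat CT/MRI scan according to iRECIST (iCPD), all induction therapy will be discontinued". Since Week 12 falls after the last planned induction dose (Day 73 or Day 64), such stops need early or off-schedule scans in control as well. That stands, and it lowers the contrast.

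Third, the magnitude rests on assumptions. That also stands. Simulation A averages 68.5 events, whereas Section 9.2 reports 63 in September 2023. If planned imaging lapsed after discontinuation, contrary to footnote i, the loss would be larger: with 60% linked stopping and half of those patients no longer scanned, power falls by about 10 points (72.8% to 62.8% by Cox).

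A reader might infer that the sponsor chose unequal imaging, or that a UV1-only stop triggers the scan. The documents state neither.

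**Conclusion.** The point holds as a minor one. On the text as extracted, one arm has a discontinuation scan that the other lacks, and those images feed the primary endpoint. A reader might infer a route to a false claim of benefit. The results do not support that: the mean shift was against UV1 in every scenario, and rejection under no effect did not rise because of the experimental-only scan. Nor is simulation A's lowest power of 0.77 a floor, because it assumes stopping unrelated to progression while the Table 5 trigger is any cause.

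With 20 to 60% discontinuing and planned imaging continuing, a fair summary is a hazard ratio higher by roughly 0 to 3% for unrelated stopping and by up to about 5% for linked stopping (5.7% in the largest log-rank case). The power loss is under 1 to about 5 points. Rate, timing, scan deadline and link to progression are all assumed, so these are illustrative ranges. Confidence is medium until Table 6 is seen on the page.

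**What to change.** Check the Table 6 imaging row on the original page. If the line is absent, reconcile the two rows so that one discontinuation-imaging rule covers both arms, with a stated window and a trigger that can occur in both. Which rule to adopt is for the sponsor. In the same edit, align the skip rule for a planned scan after an unscheduled one: footnote i in both tables uses an interval of ≤4 weeks, Section 8.1.1.1 uses <4 weeks.

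The table edit alone comes late. Last patient in was planned for H1 2022, so the last planned induction dose (Day 73) would fall about a year before version 5.0 of September 2023. Therefore also pre-specify in the SAP, before PFS is analyzed by arm and unless already there, one sensitivity analysis. It should assign central-review progression first seen on any unscheduled scan to the next scheduled assessment, or to death or the cut-off if earlier, in both arms. Report unscheduled scans by arm, with discontinuation-triggered scans shown separately. Analyses i to iv in Section 9.4.2.1 do not cover this, and that section leaves room for additions.

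Cost: one table row, a defining sentence, one more analysis and one more table to report. No added patients or visits for the analysis.
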